2.5 MitraClip Treatment

MitraClip is a device developed by Evalve and acquired by Abbott Vascular (figure 7), which reproduces the edge-to-edge surgical technique introduced into clinical practice by Alfieri (60,88,89,98,99). The surgical technique consists in suturing the free margins of both mitral leaflets at the origin of regurgitation, under direct vision with extracorporeal circulation and cardioplegic arrest. In the case of percutaneous treatment, the leaflets are joined by applying a clip under echocardiograpy guidance on the beating heart (figure 8).

Compared to the surgical edge-to-edge procedure, the percutaneous MitraClip implant offers the advantage of a reduced trauma. Of note, it also allows real time assessment of the hemodynamic effects of the clip implant by online echocardiography. In case the result is suboptimal, the clip can be repositioned or additional clips can be implanted.

The edge-to-edge surgical experience has proven to be effective and versatile. Versatility is a characteristic retained also by the percutaneous device. In fact, MitraClip implant can be performed eather in degenerative or functional MR.

The percutaneous technique was introduced in 2003 (100) and, up to now, more than 7000 patients have been treated with this device all over the world. The majority of cases has been performed in Europe. Moreover, MitraClip therapy has been evaluated in several trials and registries.

The EVEREST study (Endovascular Valve Edge-to-edge REpair of mitral regurgitation STudy) comprises a series of trials (101-115), including the first randomized controlled trial in which the percutaneous approach was compared to surgical treatment in selected patients with MR (mainly with degenerative etiology). The study results showed that after one year surgery is superior to percutaneous treatment in terms of efficacy (measured as freedom from recurrence of MR and survival), whereas the percutaneous strategy was associated with reduced blood transfusions rates (102). In a post-hoc analysis, the MitraClip therapy has proven to be non inferior to surgery in terms of effectiveness in three subgroups of patients: patients older than 70 years, those with left ventricular dysfunction and those with functional MR.

The value of the randomized cohort of EVEREST is limited because it involved only operable patients affected mainly by degenerative MR. This subset of patients does not correspond to the subjects currently undergoing MitraClip treatment in clinical practice, who in most cases have functional MR, are elderly and mostly inoperable or at high surgical risk. Furthermore, the study started when the technical experience was in a very early stage and the results were strongly influenced by the learning curve; moreover, the results of the surgical cohort were suboptimal, with in-hospital mortality approaching 6%, a value that compares unfavourably

Strictly Confidential

SICI-GISE

Rev. 01-Nov 2014

The EVEREST study has limitations that should be taken into account. Indeed, treated patients were quite healthy, with a low mean age and good EF. These patients do not represent the population of patients currently undergoing MitraClip in the real world. Indeed, most of them are elderly, with comorbidities and decreased left ventricular function. Moreover, in the majority of cases, the MitraClip is used in functional rather than in degenerative mitral valve disease. Another limitation of the EVEREST randomized trial is that the surgical outcomes were worse than expected and there was a high rate of replacement over repair. This may be due to several factors, including surgical experience of the participating centers and clinical characteristics of the patients enrolled in the study. Due to these limitations, additional controlled randomized trials focusing on the current indications for MitraClip therapy are needed.

To fill the gap between the evidence from the randomized trial and that emerging from current practice, unbiased analysis of real-world post-market registries could provide preliminary information.

The high risk registry (HRR) enrolled patients who had clinical or anatomical exclusion criteria for the MitraClip arm of the EVEREST randomized trial. The outcomes were compared with a control group represented by patients who were not treated because of anatomical contraindications to the implant. Compared to the control group, the 30-day mortality of patients treated with MitraClip was similar, while the survival at 1 year of follow-up was higher (although without statistically significant difference, figure 10)(116)

The HRR is the first study that demonstrated a prognostic benefit in high-risk patients treated with the MitraClip. Moreover,, it is noteworthy that it showed a benefit in terms of health economics: the group of patients treated with the MitraClip showed a decreased number of hospitalizations (reduced by a factor of 55% as compared to the year before implantation) with a documented benefit observed in both the degenerative and functional MR groups (figure 11). Unfortunatly, in this registry the comparator group was inadequate due to the

Strictly Confidential

fact that more than 50% of comparative patients presented problems of screening. In addition, risk assessement was augmented by less rigourous "up assignement" (117)

The ACCESS-EU registry is a prospective, observational, multicenter post-market trial. The registry collected data from 567 patients treated in 14 high-volume centers in Europe. The study had two phases: phase I completed the enrollment on April 2011 and phase II was initiated in September 2011 and finished in 2012. The main difference between the two phases is that in phase II ultrasound data were evaluated by a single core lab, while in phase I outcomes were adjudicated by individual centers.

The ACCESS registry offers a snapshot of the characteristics of patients who currently undergo the procedure in the real word: mainly elderly patients with comorbidities, high surgical risk and a high prevalence of functional mitral regurgitation (figure 12). The mean age of patients was 74 ± 10 years, with a prevalence of male gender (64%). The patients had several comorbidities, with an average surgical risk of 23 ± 18 % estimated by the logistic EuroSCORE. The etiology of MR was functional in 77% of patients, equally distributed between idiopathic and post-ischemic forms. The majority of patients were severely symptomatic (NYHA class III-IV in 85% of cases) and an ejection fraction less than 40% was present in 53% of them. Procedural success rate was 99.6%, with only 2 patients out of 566 in whom it was not possible to implant a clip. In 60% of cases, a single clip was deployed (340 patients), in 37% two clips (208 patients) and in 3% (16 patients) three or four clips. The mean procedural time was 117 ± 69 minutes. The mean length of stay in ICU was $2.5 \pm$ 6.5 days and the overall mean hospitalization was 7.7 ± 8.2 days. Mortality at 30 days was 3.4%. This mortality rate is notable low, especially if we consider that the majority of patients were at high surgical risk and affected by MR secondary to chronic heart failure. There were the following in-hospital adverse events: stroke (4 patients, 0.7%), acute myocardial infarction (4 patients, 0.7%), renal failure (24 patients, 4.2%), respiratory insufficiency (4 patients, 0.7%), cardiac arrest requiring resuscitation (10 patients, 1.8%), cardiac tamponade (6 patients, 1.1%) and bleeding (21 patients, 3.7%). In 80% of the cases, patients were discharged home, with no need of rehabilitative or home care.

At one year, there were no cases of embolization of the clip, while in 27 (4.8%) cases there was a partial clip detachment (single leaflet attachment, SLA). In 10 of these cases, SLA was treated with the implantation of an additional clip. Thirty-six (6.3%) patients with recurrent MR required surgery within 12 months after the procedure, while 19 (3.4%) required a second MitraClip procedure. At 12 months, the survival rate was 82% and 79% of patients showed residual MR less than or equal to 2+ (figure 13). Although this degree of reduction is lower than that observed after surgical repair, the persistence of a MR grade less than or equal to mild to moderate could be a reasonable therapeutic target in patients at high surgical risk. Obviously, this should not be an acceptable target for low-risk patients, for whom surgery remains the first choice.

In addition to the efficacy in reducing regurgitation, the ACCESS registry demonstrated remarkable clinical effictiveness: one year after the procedure, 71% of patients are in NYHA functional class I or II (figure 14). At one year from the index procedure, most patients have an improvement in quality of life (with a mean reduction of Minnesota Living with Heart Failure Questionnaire of -13.5 ± 20.5 points, from 41 to 28) and a gain in functional capacity (mean increase of 59 ± 120 meters from baseline at the six-minute walking test).

Strictly Confidential

In conclusion, the ACCESS registry showed that patients currently treated in Europe are different from those originally enrolled in the EVEREST study: they are older, with more comorbidities, and more frequently their MR has a functional etiology. Despite the risk profile of these patients is higher as compared to the EVEREST trial population, the procedure remains safe and effective, with satisfactory results 6 months after treatment. Although the ACCESS-EU results currently available are limited to one year of follow-up, we know from the EVEREST II trial that the hemodynamic results obtained at 6 months remain stable over time (up to 3 years after the procedure), since the risk of failure tends to run out within 6 months from implantation. Undoubtedly, the data from the registry are insufficient to fully assess the exact clinical role of the procedure. However, randomized trials in which the MitraClip will be compared to standard medical therapy has began enrollment in 2013 and will increase our knowledge regarding this issue.

2.6 Study Patient selection Mitraclip Treatment

2.6.1 Clinical Guidelines

The recent guidelines of the European Society of Cardiology consider the MitraClip as a potential therapeutic intervention in selected patients affected by severe symptomatic mitral regurgitation in case they are at high surgical risk or inoperable (118). The class assigned to this indication is IIb (evidence C), due to the lack of results from adequate randomized trials designed to guide treatment decisions in the real world. Compared to the reccommendations for surgical treatment in degenerative MR, the role of MitraClip in these patients is confined to very high risk patients otherwise inoperable. In the case of isolated FMR, MitraClip has received the same reccomendation level and class of surgery. Registries and observational data have shown that the MitraClip implantation is effective in about 70-80% of patients, with limited periprocedural risk, certainly lower than that of surgery, expecially in elderly patients with comorbidities or severe left ventricular dysfunction.

The screening selection process for Mitraclip implantation has to be reserved to expert centers owning an integrated multidisciplinary structure (Heart Team) including interventional cardiologists, cardiac surgeons, echocardiographists, anesthesiologists and heart failure specialists. The presence of surgeons in the decision-making process is essential to characterize the individual risk and to evaluate alternative therapeutic strategies, in the case of either functional or degenerative MR. The centers performing the MitraClip intervention must also have experience in treating patients with heart failure and have to be in connection with a regional hospital network (experienced with heart failure treatment) in order to monitor medical therapy and follow-up of patients implanted. The integration and coordination between hospital and territory is essential particularly for the treatment of patients at higher risk.

In the decision flow-chart, we identify three fundamental sequential steps: the indication for treatment of MR, the evaluation of surgical risk and the feasibility of the transcatheter procedure. All these steps are extremely critical and require specific experience and a multi-disciplinary approach to provide a decision free from biases and to offer a patient-individualized therapy option.

Strictly Confidential

Specifically, since in low-risk patients surgical repair intervention is known to be associated with a favorable prognostic impact (in degenerative pathology), it remains the treatment of choice in the majority of patients.

Based on the available data, and in view of the limited experience which may underestimate potential downsides, the current indications for MitraClip therapy should be limited to the treatment of symptomatic patients with MR refractory to medical therapy and deemed at high surgical risk or inoperable by surgeons proficient in mitral valve surgery and working in istitutions with a high-volume mitral surgical programs. These indications are in agreement with those outlined in the recent European Society of Cardiology guidelines (47,119)

In selected candidates, the MitraClip procedure appears to be associated with an improvement of life quality, a chance for reverse left ventricular remodeling, an increase of functional capacity and a reduction of hospitalizations. Therefore, MitraClip therapy may play a significant role in the field of non-pharmacological therapy of heart failure and mitral valve disease.

3 CLINICAL STUDY DESIGN & METHODOLOGY

3.1 Clinical Study Overview

Single arm, multi-center, retrospective and prospective study collecting clinical and health economic data from patients undergone/undergoing treatment with the MitraClip® in Hospitals linked to the GISE registry. Patients are selected upon clinical conditions and severity of MR.

3.2 Study Objectives

To collect real world data in order to further evaluate safety and efficacy of MitraClip[®]. A dedicated web-based CRF will be constructed including demographic, clinical and outcome data. A section on health economics information (resource consumption in hospital and in the year after the procedure) will be added to the clinical evaluation.

3.3 Study Endpoints

Safety endpoints: collection of safety data (MACCE and mortality) at 30days from the index procedure.

Efficacy endpoints:

- collection of early (<30d) efficacy: reduction of MR, device success, procedural resource utilization (refer to the CRF).
- collection of long-term (6m, 1y) efficacy data including survival, freedom from recurrent MR, and other health economic data (refer to the CRF)

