3.3.1 Safety and Efficacy Data Analysis

The safety and efficacy endpoints of the transcatheter procedures will be assessed by monitoring the patient's clinical status accordingly to the clinical investigational plan and by recording the echocardiographic parameters. Safety assessments will consist of recording of all adverse events, and regular monitoring of hematology and blood chemistry parameters and vital signs. These parameters are evaluated during the patient's follow-up visits.

Follow-up analysis will include both safety and efficacy analyses mentioned above, at each of the post-procedure intervals. Overall mortality rate will be determined at the end of the study.

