9.2 Analysis Population

All patients who are successfully registered will be included in the analysis.

Strictly Confidential

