9.3 Sample Size Calculations and Assumptions

Being this an observational registry aiming at quantifying effect estimates without direct comparisons to literature benchmarks, we proceeded without a formal power analysis. As the main analysis is a pooled analysis of all included patients, an overall and comprehensive analysis is planned as the primary analytical approach to reflect real-world patients and practice.

.9.4 Statistical Analyses

Continuous endpoints will be summarized by presenting the total number of patients, mean, standard deviation, median, minimum, and maximum. Tabulation of categorical parameters will include counts and percentages. The outcomes will be summarized as both a discrete and a continuous variable using the method described above. Survival analysis will be performed with the Kaplan-Meier method. Statistical inference will be based on the computation of 95% confidence intervals using the adjusted Wald method. Additional analyses will involve key subgroups defined according to baseline and and procedural features, with statistical significance set at the 5% 2-tailed level. Specifically, Student t, Fisher exact, and log-rank tests will be used for such bivariate analyses, whereas multivariable linear regression, logistic regression, and Cox proportional hazard analyses will be used to adjust for confounders.

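### Section 9.4 names Kaplan-Meier as its only estimator of risk over time and does not say how death is handled for freedom from recurrent MR or for visit-wise functional means

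*Protocol*

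**What the plan says.** Section 3.3 lists the long-term efficacy data as "collection of long-term (6m, 1y) efficacy data including survival, freedom from recurrent MR", followed by health economic data. Recurrence is not defined there, and nothing says what a death before recurrence counts as.

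Section 9.4 states: "Survival analysis will be performed with the Kaplan-Meier method". For comparisons it adds that "Student t, Fisher exact, and log-rank tests will be used for such bivariate analyses", and that "Cox proportional hazard analyses will be used to adjust for confounders" (after linear and logistic regression). Categorical parameters get counts and percentages, and confidence intervals use the adjusted Wald method. No competing-risk estimator and no composite with death is named.

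For measurements, "Continuous endpoints will be summarized by presenting the total number of patients, mean, standard deviation, median, minimum, and maximum". Section 3.3.1 applies the safety and efficacy analyses "at each of the post-procedure intervals", and section 9.2 says: "All patients who are successfully registered will be included in the analysis". 6MWT and MLHFQ are collected at baseline, 30 days, 6 months and 12 months (sections 3.10.1 and 3.10.5 to 3.10.7). Table 1 continues the follow-up visits yearly to 5 years.

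On mortality, section 2.5 reports from a European post-market registry of the same device: "At 12 months, the survival rate was 82% and 79% of patients showed residual MR less than or equal to 2" (that is, grade 2+).

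**The concern.** A patient who dies can no longer be seen to recur. Kaplan-Meier with deaths censored treats the dead as if they remained at risk like the living, so its complement estimates recurrence in a setting without death. It does not estimate the proportion of treated patients who actually recur, and that proportion is what a registry reader will take the figure to be. The direction is known: recurrence is overstated and freedom from recurrence understated.

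For 6MWT and MLHFQ the issue is the denominator. Patients who die have a baseline value but no 12-month value. If those who die start out worse, comparing the two visit means shows an apparent gain even when no survivor changes.

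**Working it through.** The protocol gives no recurrence rate, precision figure or power calculation for this endpoint, so there is no planned figure to reproduce. The check is an illustration.

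**Inputs**
- One-year survival 82% (section 2.5, cited registry). Death hazard m = −ln(0.82) = 0.198 per year.
- One-year recurrence by one minus Kaplan-Meier, deaths censored: assumed 10% and 21%. The 21% is the complement of the 79% in section 2.5. That figure is residual MR at one visit, not cumulative recurrence, so using it is an assumption.
- Recurrence hazard l = −ln(0.90) = 0.105 or −ln(0.79) = 0.236 per year.
- n = 500 (Synopsis, approximate).

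**Formulas** (independent constant hazards)
- One minus Kaplan-Meier: 1 − exp(−l·t)
- Cumulative incidence with death competing: l/(l+m) × [1 − exp(−(l+m)·t)]

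**At 1 year**
- 10% case: 0.105/0.304 × [1 − exp(−0.304)] = 9.1%, against 10.0%. Gap 0.9 points.
- 21% case: 0.236/0.434 × [1 − exp(−0.434)] = 19.1%, against 21.0%. Gap 1.9 points. A simulation of 1,000,000 patients also gave 19.1%.
- At 6 months the 21% case gives 10.6% against 11.1%, a gap of 0.5 points.
- Varying one-year survival over 75% to 90% and recurrence over 10% to 30% (assumed ranges), the one-year gap runs from 0.5 to 3.7 points.

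**Recurrence confined to the first 6 months**, as the failure pattern in section 2.5 suggests (hazard doubled, t = 0.5)
- 10% case: l = 0.211, cumulative incidence 9.5%. Gap 0.5 points.
- 21% case: l = 0.471, cumulative incidence 20.0%. Gap 1.0 point.
- With no later recurrence, the gap stays at that size.

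**Recurrence at a constant rate for 5 years**
- 10% case: 27.1% against 41.0%. Gap 13.9 points.
- 21% case: 48.1% against 69.2%. Gap 21.1 points.

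**Sampling error for scale.** Adjusted Wald 95% half-width at n = 500: adjusted n = 500 + 1.96² = 503.8 and adjusted proportion = (events + 1.92)/503.8. This gives 2.7 points at 10% and 3.6 points at 21%, in each case more than the one-year gap.

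**Role of death, one year, 21% case**
- Deaths censored: 79.0% free.
- Death competing: 100 − 19.1 = 80.9% without observed recurrence, including those who died first.
- Death as failure: 0.82 × 0.79 = 64.8% alive and free.

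**Functional outcomes.** 500 × 0.82 = 410 patients at most can have a 12-month value; about 90 of the 500 with a baseline cannot, because of death alone. The documents give no 6MWT or MLHFQ values by later vital status, so the effect on the mean cannot be calculated.

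**The case against.** Nowhere does the protocol say that freedom from recurrent MR will be estimated by Kaplan-Meier, or that deaths will be censored. The Kaplan-Meier sentence may concern survival alone. Recurrent MR is read from echocardiography at scheduled visits, and section 9.4 provides percentages with adjusted Wald intervals, so a visit-wise proportion is open. Death could also count as failure, as in the composite of the randomised trial described in the Synopsis. Under neither reading does this bias arise. Handling of death is commonly left to a statistical analysis plan, which section 3.11 mentions and which is not shown. The bias also runs against the device and is smaller than sampling error at 1 year. All of this stands, and it limits the point.

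It does not remove it. Section 9.4 is specific enough to name tests and interval methods, it names one estimator of risk over time, and section 3.3 separates recurrence from survival, so censoring at death is what an analyst would do by default. A visit-wise percentage avoids this bias but describes only living attendees.

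Three stronger readings are tempting and not supported:
- That Kaplan-Meier is the only time-to-event method. Log-rank tests and Cox models are named in the same paragraph.
- That the error grows to 14 or 21 points by year 5. This needs a constant recurrence hazard, whereas section 2.5 says failure occurs mainly in the first 6 months, and section 3.3 sets the endpoint at 6 months and 1 year.
- That functional gain is shown to be inflated. Only a likely direction can be given. Section 9.4 does require the number of patients with each summary, so a shrinking denominator would be visible.

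**Conclusion.** The point holds in a limited form. The protocol leaves the role of death unstated for freedom from recurrent MR, and its only named estimator of risk over time would, with deaths censored, overstate the share of treated patients who recur. The overstatement is about 1 to 2 points at 1 year under constant hazards, or about 0.5 to 1 point if recurrence is confined to the first 6 months. This rests on 82% one-year survival, an assumed 10% to 21% recurrence, and independence of death and recurrence. A large 5-year gap arises only if recurrence continues at a constant rate.

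The choice of definition matters more than the censoring bias: in the 21% illustration the one-year result is 64.8% if death is a failure and 79.0% to 80.9% otherwise. Visit-wise 6MWT and MLHFQ means compare everyone at baseline with at most about 410 of 500 at 12 months. This may flatter functional gain by an amount the documents do not let one quantify.

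**What to change.** In section 9.4:
- Keep Kaplan-Meier for all-cause death and for the composite of being alive and free from recurrent MR.
- Report recurrent MR as Aalen-Johansen cumulative incidence with death as a competing event.
- State that the Cox models already planned are cause-specific for this endpoint.
- For 6MWT, MLHFQ and MR grade, report within-patient change in patients with both values, next to the numbers dead and missing at each visit.

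The cost is wording and slightly more output to explain. Survival and the visit measurements are already collected, so no new data are needed.
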